12.2.8 Calculation and derivation of ICU-free days

The number of days alive and ICU-free up to and including Day 15 (over 14 days) will be derived from the assessment detailed in Section 7.6.9.

12.2.9 Calculation and derivation of shock-free days

The number of shock-free days up to and including Day 15 (over 14 days) will be derived from the assessment detailed in Section 7.6.10.

12.3 Calculation or derivation of pharmacokinetic variables

The PK analyses will be performed at AstraZeneca Research & Development. The actual sampling times will be used in the PK calculations. Full details of the population PK and PK-PD analysis will be given in the Pharmacokinetic Analysis Plan approved before the start of analysis. Results will be reported in a separate report.

12.4 Calculation or derivation of pharmacodynamic variables

12.4.1 Population analysis of pharmacokinetic/pharmacodynamic variables

Full details of the population PK and PK-PD analysis will be given in the Pharmacokinetic Analysis Plan approved before the start of analysis. Results will be reported in a separate report.

12.4.2 Calculation or derivation of the relationship between pharmacokinetic and pharmacodynamic variables

The relationship between drug serum concentration and effect of PD variables will be presented graphically. If appropriate, concentration-effect relationships will be explored.

12.4.3 Calculation or derivation of the relationship between pharmacokinetic and efficacy variables

The relationship between drug serum concentration and efficacy variables will be presented graphically. If appropriate, concentration-effect relationships will be explored.

12.4.4 Calculation or derivation of the relationship between pharmacokinetic variables and adverse events

The relationship between drug serum concentration and AEs will be explored.

12.5 Calculation or derivation of pharmacogenetic variables

Not applicable.

12.6 Calculation or derivation of health economics variables

Not applicable.

13. STATISTICAL METHODS AND SAMPLE SIZE DETERMINATION BY ASTRAZENECA

13.1 General principles

A comprehensive SAP will be finalised before the last patient visit. All statistical analyses will be performed by PAREXEL. Any deviations from those analyses presented here and/or in the SAP will be detailed in the clinical study report. All outputs will be produced using SAS[®] version 9 or later in accordance with AstraZeneca standards.

All study data will be analysed after the 28-day follow up is complete for all patients. A further analysis will be performed using the Day 90 assessment to understand longer-term patient outcomes (survival and HRQoL).

The following efficacy endpoints will be subject to formal statistical analysis: VFDs, 7-day mortality, 28-day mortality, mortality at Day 90, organ failure-free days, shock-free days and ICU-free days. All other data will only be summarised.

All efficacy data will be summarised and analysed using the per protocol (PP) population. Additionally, an ITT analysis of the endpoints listed above for formal analysis will also be undertaken using the ITT population.

For each of the endpoints subject to statistical analysis the following statistical comparisons will be performed: AZD9773 dose 1 versus placebo, AZD9773 dose 2 versus placebo, and combined AZD9773 dose arms 1 and 2 versus placebo. Although there are three primary comparisons, this is an exploratory Phase IIb study and consequently no adjustment for multiple comparisons will be made.

Unless stated below, no imputation of missing data will be performed. All data recorded on the database will be included in data listings. Any spurious or erroneous data will be queried and followed up until satisfactorily resolved.

The nominal significance level used for this study will be 10% one-sided. However, it is important to note that the study has only been sized based on VFDs over 28 days; this study is not powered to detect a statistically significant difference in 7-day mortality, 28-day mortality or mortality at Day 90. In this case the confidence intervals (CIs) will provide a guide to the possible range of the true treatment effect. This may also be the case for the other secondary endpoints.

Demography data will be summarised using the PP and ITT populations and safety data will be summarised using the safety population. For all summaries of change from baseline, baseline is defined as the latest non-missing assessment prior to first study drug infusion.

The results of the genetic research will not form part of the Clinical Study Report for this study. The number of patients who will agree to participate in the genetic research is unknown. It is therefore not possible to establish whether sufficient data will be collected to

allow a formal statistical evaluation or whether only descriptive statistics will be generated. A separate SAP will be prepared where appropriate. This also applies to the blood samples obtained for use in future sepsis biomarker assays that may become available. In addition, the analysis of the multiplex assay for exploratory chemokines and the plasma renal panel for exploratory analysis are not planned to be included in the Clinical Study Report for this study.

The results from any exploratory biomarker analyses may be pooled with biomarker data from other studies on AZD9773 to generate or validate emerging hypotheses.

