13.2.3 Per-Protocol population

This population will be a subset of the ITT population including only patients without important detected protocol deviations affecting the efficacy endpoints. Patients will be summarised according to the actual treatment first received.

The patients with important protocol deviations will include those failing the inclusion/exclusion criteria as well as any patients taking medications that are prohibited during the study treatment period (see Section 6.5.2). Prior to clean file and code break, the patients to be excluded from the PP population will be reviewed and agreed by the study team physician and statistician.

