13.3 Methods of statistical analyses

13.3.1 Demographics, baseline characteristics, and concomitant medications

Demographic data, medical history, surgical history, Charlson Comorbidity Scale, physical examination (including dermal examination and lung auscultation), and key concomitant medications will be summarised. Concomitant medications will be coded using the AstraZeneca Drug Dictionary.

Patients who have to discontinue study treatment due to the administration of immunosuppressant medications, corticosteroids other than for adrenal replacement therapy, and anti-TNF antibodies during Days 1 to 6 will be summarised by treatment group.

Baseline disease characteristics including APACHE II Score, Glasgow Coma Score, TNF α , time of initial antibiotic dose relative to the qualifying organ failure and the number of patients with shock, on a ventilator, on vasopressors, with a positive culture or with renal impairment will also be summarised.

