13.3.6 Organ failure-free days, shock-free days, and ICU-free days

Organ failure-free days, shock-free days, and ICU-free days will be summarised and analysed in the same way as for VFD (see Section 13.3.4).

13.3.7 7-day mortality, 28-day mortality and mortality at Day 90

Seven-day mortality and 28-day mortality will be summarised by treatment group. The formal analysis will be undertaken for each the comparisons: AZD9773 dose 1 versus placebo, AZD9773 dose 2 versus placebo, AZD9773 dose 1 and 2 versus placebo separately using a Cochran-Mantel-Haenszel test in which the test will be stratified using the same covariates as for VFD. The corresponding relative risk, two-sided 80% CI and one-sided p-value will be calculated using the procedure PROC FREQ in SAS. Additionally, a two-sided 95% CI and two-sided p-value will also be presented.

An unstratified analysis will also be performed for the PP and ITT populations. Additionally, for the PP population, the impact of other baseline variables (examples include baseline TNF, Xigris use prior to study treatment and presence of shock at baseline) on the treatment comparisons will be explored by undertaking a series of analyses for each of the levels of these baseline variables separately, and the relative risks along with the associated two-sided 80% CIs from these analyses will be presented graphically.

In the event that the 7-day mortality and 28-day mortality status is unknown for some patients, they will be excluded from the PP population. However, for the ITT population they will be included as though they had died. Further sensitivity analyses may be undertaken depending on the number of such patients.

A Kaplan-Meier curve of time to death will also be produced and both a stratified (using the same covariates as for the analysis of 7 and 28-day mortality) and unstratified log rank test will be undertaken. If the 7-day or 28-day mortality status is unknown for some patients, they will be censored at the last known date the patient was alive.

Mortality at Day 90 will be considered in the same way as 7-day and 28-day mortality.

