13.4 Determination of sample size

The sample size has been based on the primary outcome variable of VFDs over 28 days. The Phase IIb study in 81 patients with D-CytoFab has been used as an estimate of the between-patient SD (11.380). Assuming this SD holds for the current study, then 100 patients per group will provide 90% power to detect an underlying true difference in means between a dose of AZD9773 and placebo of 4.2 days using a 10% one-sided significance level.

Given this is an exploratory Phase II study, a 10% one-sided significance level is considered appropriate as this implies a 1 in 10 chance of a false positive finding which is consistent with the aim in Phase II of identifying a promising therapy.

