 - If the infusion is stopped or decreased, wait until signs/symptoms have been stable for 15 minutes prior to restarting or increasing rate.
 - Wait 15 minutes and consider restarting infusion at half the initial rate (equivalent to doubling the time planned for the infusion).
- (b) Treatment options
 - Signs/symptoms including but not limited to:
 - Hypotension (fluids, pressors).
 - Bronchospasm (inhaled albuterol, antihistamines, epinephrine, steroids).
 - Angioedema (intubation/airway management, antihistamines, epinephrine, steroids).
 - Hyperthermia (cooling measures, acetaminophen, antihistamines, steroids, epinephrine).
 - Rash/urticaria (antihistamines, steroids, epinephrine).
 - Vomiting (antiemetics).

- Symptoms such as pruritis, chills, myalgias, arthralgias (acetaminophen, antihistamines, steroids, epinephrine).
- Treatment/drug, suggested doses including, but not limited to:
 - Epinephrine (1:1000 0.1 to 0.5 mL subcutaneously; repeat as necessary).
 - Diphenhydramine (25 to 50 mg iv; repeat as necessary).
 - Albuterol/salbutamol (0.5 mL of 0.5% solution, nebulised; repeat as necessary).
 - Methylprednisolone (20 to 40 mg iv).
 - Acetaminophen (625 mg orally if oral route can be tolerated).
 - Pressors (eg, dopamine, epinephrine, norepinephrine to maintain organ perfusion, SBP >90 mmHg, mean arterial pressure >70 mmHg).
 - Oxygen to keep oxygen saturation >92%; airway and ventilation setting adjustment to maintain normal ventilation.
 - iv fluids (500 to 1000 mL/hour to help maintain adequate perfusion).

Delayed infusion reactions

- Investigator discretion with following suggested treatment options:
 - Acetaminophen.
 - Steroids (orally, or iv if severe).
 - Antihistamines (orally, or iv if severe).
 - Monitoring; human anti-sheep antibodies, auto-antibody screen, routine laboratory measurements and total IgE.

VI Monitoring of suspected infusion reactions

- (a) Standard medical monitoring for an ICU setting to include at least the following:
 - Vital signs every 2 minutes until stable.
 - Clinical examination every 5 minutes until stable.
 - Laboratory parameter measurements to consider:

- Serum tryptase, IgE and quantitative eosinophil count, 20 to 60 minutes post suspected infusion or hypersensitivity reaction and repeated on blood draw at Day 29.

THIS IS A PRINTED COPY OF AN ELECTRONIC DOCUMENT. PLEASE CHECK ITS VALIDITY BEFORE USE.

Clinical Study Protocol Appendix E

Drug Substance	AZD9773
Study Code	D0620C00003

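### The lead efficacy analysis uses a per-protocol set that drops patients for post-randomisation events, so the lead VFD comparison is not protected by randomisation; ITT should lead

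*Protocol*

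**What the plan says.** Section 13.1 and the synopsis put the PP set first: "All efficacy data will be summarised and analysed using the per protocol (PP) population". ITT follows as an addition: "Additionally, an ITT analysis of the endpoints listed above for formal analysis will also be undertaken using the ITT population". The explorations by baseline variable in Sections 13.3.4 and 13.3.7 are planned for PP only.

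Section 13.2.3 defines PP as a subset of ITT "including only patients without important detected protocol deviations affecting the efficacy endpoints". Important deviations are to include failures of the entry criteria, "as well as any patients taking medications that are prohibited during the study treatment period", with a pointer to Section 6.5.2. Patients are grouped by the treatment they first received. The study team physician and statistician agree the exclusions before clean file and code break.

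Section 13.3.7 adds a further reason. Of patients whose 7-day or 28-day mortality status is unknown it says "they will be excluded from the PP population", whereas ITT counts them as deaths.

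On size, Section 13.4 says that "100 patients per group will provide 90% power to detect an underlying true difference in means" of 4.2 VFDs, at 10% one-sided. The synopsis equates 100 per group with patients randomised, and Section 6.2.1 says that withdrawn patients are not replaced.

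**The concern.** All three comparisons test active drug against placebo for superiority. Randomisation makes the arms comparable only while every randomised patient is counted in the arm assigned. Use of a prohibited drug and loss of vital status both occur after randomisation, and treatment may influence either. If such exclusions differ between arms and the excluded patients have a different prognosis, the PP difference mixes the drug effect with the effect of selection.

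The two sets also treat unknown mortality status in opposite ways: it is removed in PP and counted as death in ITT. The two results could disagree, and the protocol's ordering would then favour PP. Section 4.2 says the study is to determine which regimen goes forward to work on 28-day mortality, at a 10% one-sided level without multiplicity adjustment. A small selection effect could therefore matter to that choice.

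**Working it through.** **1. The plan's power figure.** Inputs from Section 13.4: SD 11.380, difference 4.2, 100 per arm, one-sided 10% (z = 1.2816).

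- SE = 11.38 × √(2/100) = 1.609 days.
- Power = Φ(4.2/1.609 − 1.2816) = Φ(1.328) = 90.8%. The stated 90% is reproduced.
- Number needed for 90% power = 2 × 11.38² × (1.2816 + 1.2816)² / 4.2² = 96.5, so 97 per arm.

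**2. Power if PP leads.** The protocol gives no exclusion rate, so these shares are assumptions. The formula is the same, with n evaluable per arm and the unadjusted SD.

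| Excluded | n per arm | Power |
|---|---|---|
| 0% | 100 | 90.8% |
| 3% | 97 | 90.1% |
| 5% | 95 | 89.7% |
| 10% | 90 | 88.4% |
| 15% | 85 | 87.0% |
| 20% | 80 | 85.4% |

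The slack is 3 patients per arm. Power is more than 2 points below 90% only at 88 or fewer per arm, that is, 12% or more excluded.

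**3. Bias from unequal exclusion, with no true effect.** Let f be the share excluded in an arm and g the amount by which retained patients exceed excluded ones in mean VFDs, taken as equal in both arms. The retained mean is then the arm mean plus f × g, so the bias in active minus placebo is (f_active − f_placebo) × g. One-sided error = 1 − Φ(1.2816 − bias/SE), with SE = 1.609. All values of f, and g = 8, are assumptions.

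| Active / placebo excluded | Bias (days) | One-sided error |
|---|---|---|
| 10% / 10% | 0 | 10% |
| 10% / 5% | (0.10 − 0.05) × 8 = +0.40 | 1 − Φ(1.033) = 15% |
| 10% / 0% | 0.10 × 8 = +0.80 | 1 − Φ(0.784) = 22% |
| 5% / 10% | −0.40 | 1 − Φ(1.530) = 6% |

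Using the reduced group sizes in the SE changes little: 14.9% for 10%/5% and 21.3% for 10%/0%. A shift of 0.40 days is 0.40/4.2, or about 10% of the design difference.

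**4. A different parameterisation.** Take an overall mean of 9.8 VFDs (the earlier D-CytoFab study's placebo mean, Section 2.4) and excluded patients averaging 0 to 4.9 VFDs. Excluding 10% versus 5% gives a bias of 0.6 to 0.3 days and error of 17% to 13%. Excluding 15% versus 5% gives 1.2 to 0.6 days and 29% to 18%.

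**5. The steroid passages.** Section 13.3.1 lists "corticosteroids other than for adrenal replacement therapy, and anti-TNF antibodies during Days 1 to 6" among reasons for stopping study treatment. Sections 6.1 and 6.5.2 prohibit immunosuppressants, with examples, and anti-TNF antibodies; neither names corticosteroids. Appendix I does list corticosteroids among immunosuppressive agents. Appendix D includes "Methylprednisolone (20 to 40 mg iv") among the options for infusion reactions. Whether a patient given steroids on Days 1 to 6 counts as a PP exclusion therefore depends on which passage is followed.

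**The case against.** The safeguards are real. PP exclusions are fixed before code break. A full ITT analysis of every formally tested endpoint, VFDs included, is already planned by randomised arm. Section 5.3 requires follow-up of ineligible randomised patients because of it. The protocol never calls PP primary or says that PP alone decides success. Failure of entry criteria is a baseline feature. The study is declared exploratory. All of this stands, and it makes the problem one of ordering. But blinded review does not help when the excluding event itself depends on treatment, and the text does put PP first for all efficacy data.

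Three stronger readings are tempting, and the documents support none of them.

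- **The trial fails to hold its stated power.** The 90% reproduces, and any loss depends on an exclusion rate that is not given. The ANCOVA could also recover some precision: if its covariates explained 10% of the variance (an assumption), 90 PP patients per arm would match 100 unadjusted, since 90/0.9 = 100.
- **The bias favours active drug.** Sections 2.1.4 and 2.4 report comparable adverse event numbers on active drug and placebo in the earlier studies, and nothing shows that prohibited-drug use would be higher on active drug. The last row of the bias table shows the opposite case.
- **Patients who react to active drug leave the lead analysis through steroid use.** Section 13.2.3 points to Section 6.5.2, which does not name corticosteroids. Section 13.3.1 describes only a summary of treatment discontinuations. Stopping treatment for a reaction is not itself listed as a PP exclusion.

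**Conclusion.** The concern holds as a matter of which set leads. The protocol gives the lead in a superiority comparison to a set that excludes on post-randomisation events and groups by treatment first received, so the lead VFD result lacks the protection of randomisation.

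The size cannot be fixed from the documents. It is zero if similar patients are excluded equally. With an assumed 8-VFD gap it is about 0.4 days and 15% one-sided error at 10% versus 5%, and about 0.8 days and 22% at 10% versus 0%; the last case assumes no placebo exclusions at all. The direction is unknown.

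The power statement is right for 100 per arm. What can be said is that no allowance for PP exclusions is stated, so a PP-led analysis drops below 90% with fewer than 97 evaluable per arm.

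**What to change.** In Sections 13.1 to 13.3 and the synopsis, name ITT (all randomised patients, by randomised arm) as the lead set for VFDs, the other formally tested endpoints and the plots by baseline variable. Keep PP as a supportive analysis. In Section 13.4, say that the 90% power refers to the ITT set. Separately, reconcile Section 13.3.1 with Sections 6.1 and 6.5.2 on corticosteroids, since the answer decides who counts as a PP exclusion.

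The cost is wording. The ITT analyses of the formal endpoints are already planned; only the plots by baseline variable would have to be run on a different set. No change in N is needed. By contrast, keeping PP as lead with 97 evaluable per arm would mean randomising 97/0.95 = 103 per arm at an assumed 5% exclusion, or 97/0.90 = 108 at 10%. The downside of leading with ITT is slight dilution from ineligible or undosed patients.

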13.2 Description of analysis sets

The following three analysis sets will be defined for this study.

13.2.1 Safety population

All patients who start an infusion of study drug will be included in the safety population and data will be summarised according to the actual treatment first received.

13.2.2 Intention-to-treat population

All randomised patients will be included in the ITT population and data will be analysed and summarised according to the randomised treatment.

13.2.3 Per-Protocol population

This population will be a subset of the ITT population including only patients without important detected protocol deviations affecting the efficacy endpoints. Patients will be summarised according to the actual treatment first received.

The patients with important protocol deviations will include those failing the inclusion/exclusion criteria as well as any patients taking medications that are prohibited during the study treatment period (see Section 6.5.2). Prior to clean file and code break, the patients to be excluded from the PP population will be reviewed and agreed by the study team physician and statistician.

13.3 Methods of statistical analyses

13.3.1 Demographics, baseline characteristics, and concomitant medications

Demographic data, medical history, surgical history, Charlson Comorbidity Scale, physical examination (including dermal examination and lung auscultation), and key concomitant medications will be summarised. Concomitant medications will be coded using the AstraZeneca Drug Dictionary.

Patients who have to discontinue study treatment due to the administration of immunosuppressant medications, corticosteroids other than for adrenal replacement therapy, and anti-TNF antibodies during Days 1 to 6 will be summarised by treatment group.

Baseline disease characteristics including APACHE II Score, Glasgow Coma Score, TNF α , time of initial antibiotic dose relative to the qualifying organ failure and the number of patients with shock, on a ventilator, on vasopressors, with a positive culture or with renal impairment will also be summarised.

13.3.2 Protocol deviations

Important protocol deviations will be summarised by treatment group.

13.3.3 Pharmacokinetics

Serum concentrations for AZD9773 specific and total Fabs will be listed by treatment group.

13.3.4 Ventilator-free days

Summary statistics (mean, median, standard deviation [SD], minimum, and maximum) of VFDs over 28 days will be presented by treatment group. Missing data will be handled using a last observation carried forward (LOCF) approach when calculating VFDs for each patient. A histogram of VFD will also be produced for each treatment group.

For the formal statistical analysis, an analysis of covariance model will be fitted for VFDs allowing for treatment group and the following baseline covariates:

APACHE II score (four categories based on the quartiles of the baseline score), age (two categories: <60 and 60 or older), region (three categories: Australia, North America [Canada & USA] and All Other) and an indicator variable if the patient was on mechanical ventilation at baseline (two categories: yes or no).

The difference in VFDs for each of the comparisons: AZD9773 dose 1 versus placebo, AZD9773 dose 2 versus placebo, AZD9773 dose 1 and 2 versus placebo will be presented in terms of the difference in the Least Square Means (LSMeans) and the associated two-sided 80% CI and one-sided p-value. Additionally, a two-sided 95% CI and two-sided p-value will also be presented.

For the PP population, the effect of other baseline variables (examples include baseline TNF, Xigris use prior to study treatment and presence of shock at baseline) on the treatment comparisons will also be explored via a series of analyses including the covariates as specified above for each of the levels of these baseline variables separately. The difference in the treatment LSMean and the associated two-sided 80% CI from these analyses (along with the results from the baseline covariates fitted in the statistical analysis above) will be presented graphically on the same plot. Additionally, an analysis of variance will also be performed for the PP and ITT populations (with no covariates and only treatment as a factor).

VFDs at Day 15 (over 14 days) will be analysed in a similar manner to above.

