For the formal statistical analysis of all endpoints apart from mortality, an analysis of covariance model will be fitted allowing for treatment group and the following baseline covariates: Acute Physiology and Chronic Health Evaluation (APACHE) II score (4 categories based on the quartiles of the baseline score), age (2 categories: <60, ≥60), region (3 categories: Australia, North America [Canada & USA] and All Other) and an indicator variable if the patient was on mechanical ventilation at baseline (2 categories: yes or no). The

difference for each of the comparisons will be presented in terms of the difference in the Least Square Means (LSMeans) and the associated two-sided 80% CI and one-sided p-value. Additionally, a two-sided 95% CI and two-sided p-value will be presented.

In terms of these endpoints for the PP population, the effect of other baseline variables (examples include baseline TNF α , Xigris use prior to study treatment and presence of shock at baseline) on the treatment comparisons will also be explored via a series of analyses including the covariates as specified above for each of the levels of these baseline variables separately. The difference in the treatment LSMean and the associated two-sided 80% CIs estimated for each level of the covariates will be presented graphically on the same plot. Additionally, an analysis of variance will also be performed for the PP and ITT populations (with no covariates and only treatment as a factor).

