6.2.1 Procedures for randomisation

Patients will be randomised to treatment following verification of conformance with eligibility criteria at screening. Central randomisation via IVRS will be used to allocate patients to treatment groups (AZD9773: dose 1, dose 2, placebo) in a 1:1:1 ratio and avoid selection bias.

Randomisation will be performed in blocks based on a computer-generated randomisation scheme provided by AstraZeneca. The size of randomisation blocks will not be disclosed to the study centres. Randomisation will not be stratified. The randomisation scheme will randomly assign the study drug to the randomisation numbers.

Randomisation codes will be assigned strictly sequentially as patients become eligible for randomisation. Randomised patients who terminate their study participation for any reason, regardless of whether the study drug was taken or not, will retain their randomisation number. The next patient will be given the next randomisation number.

Patients who are withdrawn after randomisation will not be replaced.

Sections [6.3.1](#) and [6.3.2](#) describes procedures for blinding and breaking the blind.

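### Age and APACHE II enter the VFD ANCOVA as coarse categories, although both are available as numbers; the analysis is valid but gives up a little precision

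*Protocol*

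**What the plan says.** Protocol 13.3.4 fits an analysis of covariance to VFDs over 28 days with treatment and four baseline covariates. APACHE II is entered in "four categories based on the quartiles of the baseline score", and age is given as "age (two categories: <60 and 60 or older". The other two, region (three levels) and mechanical ventilation at baseline (yes or no), are categorical by nature. The synopsis agrees, with APACHE II in "4 categories based on the quartiles of the baseline score" and the same age cut. Section 13.3.6 applies the model to organ failure-free, shock-free and ICU-free days. The only other overall VFD model in the protocol is an analysis of variance with treatment alone.

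Both covariates exist in finer form. Section 7.2 collects date of birth, and 12.2.3 has the APACHE II score calculated electronically from the eCRF values. Section 6.2.1 states "Randomisation will not be stratified".

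The categories have other uses. Section 13.3.7 takes the same covariates as strata for the Cochran-Mantel-Haenszel and log-rank tests, and 13.3.4 plots VFD treatment differences by covariate level.

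**The concern.** A covariate earns its place in an ANCOVA by explaining outcome variance. With age cut at 60, a patient of 60 is treated like one of 85, and a patient of 25 like one of 59. Differences within a band stay in the residual, and chance imbalance within a band is not adjusted by that term. The protocol's own severity score treats risk as rising inside both bands: the APACHE II age points in Appendix E step through 0, 2, 3, 5 and 6, and the cut at 60 divides the 55-64 group, whose members all score 3.

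Had randomisation been stratified on these categories, there would be a design reason to carry them into the model. It was not. What is at stake is precision: confidence intervals for the primary and related endpoints somewhat wider than the collected data allow.

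**Working it through.** **1. The plan's own figure.** Section 13.4 uses an "estimate of the between-patient SD (11.380" days), a difference from "placebo of 4.2 days", and a test "using a 10% one-sided significance level"; it states that "100 patients per group will provide 90% power".

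- Required n per arm = 2 × (1.2816 + 1.2816)² × 11.38² / 4.2² = 96.5, so 97.
- Power at 100 per arm = Φ(4.2 / (11.38 × √(2/100)) − 1.2816) = Φ(2.610 − 1.282) = 90.8%.

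The stated figure reproduces. It uses the unadjusted SD and takes no credit for covariates.

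**2. Information kept by each cut.** For a standard normal covariate with a linear effect, the share of explained variance kept is the sum over groups of p × m², where p is the group's proportion and m its mean.

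- Quartiles: group means ±1.271 and ±0.325, so (1.271² + 0.325²)/2 = 0.861.
- Two levels cut at the median: 2/π = 0.637.
- Two levels split 30/70: 0.348² / (0.3 × 0.7) = 0.576.

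**3. Effect on the treatment comparison.** The correlations of APACHE II and age with VFDs are not in the protocol. The ranges used are assumptions: 0.1 to 0.5 for APACHE II, 0.1 to 0.3 for age, and 0 or 0.3 between the two. Example with 0.4, 0.2 and 0, as shares of total variance:

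- Categorised residual variance: 1 − 0.861 × 0.16 − 0.637 × 0.04 = 0.837.
- Continuous residual variance: 1 − 0.16 − 0.04 = 0.800.
- SE ratio: √(0.837/0.800) = 1.023.

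The table comes from simulated samples of one million, with age cut at its median. Equivalent patients = 300 × (variance ratio − 1).

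| APACHE II / age correlation with VFD | Correlation between the two | Residual variance, categorised | Residual variance, continuous | SE ratio | Equivalent patients of 300 | Power, categorised → continuous |
|---|---|---|---|---|---|---|
| 0.1 / 0.1 | 0.3 | 0.9869 | 0.9839 | 1.0015 | 0.9 | 91.1% → 91.1% |
| 0.1 / 0.1 | 0 | 0.9846 | 0.9797 | 1.0025 | 1.5 | 91.1% → 91.2% |
| 0.2 / 0.1 | 0.3 | 0.9639 | 0.9581 | 1.0030 | 1.8 | 91.6% → 91.7% |
| 0.2 / 0.1 | 0 | 0.9584 | 0.9492 | 1.0048 | 2.9 | 91.7% → 91.9% |
| 0.4 / 0.2 | 0.3 | 0.8557 | 0.8328 | 1.0136 | 8.2 | 93.8% → 94.3% |
| 0.4 / 0.2 | 0 | 0.8351 | 0.7987 | 1.0225 | 13.7 | 94.2% → 94.9% |
| 0.5 / 0.3 | 0.3 | 0.7651 | 0.7246 | 1.0275 | 16.8 | 95.6% → 96.3% |
| 0.5 / 0.3 | 0 | 0.7279 | 0.6603 | 1.0499 | 30.7 | 96.2% → 97.3% |

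If age 60 splits the sample 30/70 rather than at the median, the most extreme row changes little: 1 − 0.861 × 0.25 − 0.576 × 0.09 = 0.733, and √(0.733/0.66) = 1.054.

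**4. Check on a VFD-like outcome.** VFDs are bounded and, under 12.2.6, zero for patients who die before Day 29 or are on assisted breathing at Day 29. A simulation of 300 patients used a 0-28 outcome with 40% at zero and 15% at 28 (SD about 11) and uncorrelated covariates. The SE was 1.565 categorised against 1.554 continuous at 0.2/0.1 (0.7% larger), and 1.398 against 1.354 at 0.5/0.3 (3.3% larger).

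**The case against.** The strongest reply is that this is a preference, not an error. The synopsis and 13.3.4 agree, the categories are pre-specified and do not depend on outcome, and the comparison they produce is valid. That stands.

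A reader might also infer more than the protocol supports, in four ways.

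- **That the categories serve only the mortality tests.** They do not: 13.3.4 and the synopsis also plot VFD treatment differences by covariate level, so those levels must stay defined.
- **That nothing is gained by cutting.** Quartiles allow a threshold or plateau in the APACHE II effect, which a straight line does not. For a bounded composite with many zeros, linearity is not established. A strictly linear term is therefore not guaranteed to be better, and the 58-64% and 86% figures hold only for a roughly normal covariate with a linear effect.
- **That the quartiles will differ between the PP and ITT analyses.** The protocol does not say which set defines them. That is a detail commonly left to the SAP, so it is no finding here.
- **That the trial is underpowered as a result.** Section 13.4 sizes it on the unadjusted SD, and any useful covariate adds to that, cut or not.

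Age is also partly counted inside APACHE II, so the age cut discards less than its stand-alone share suggests. The rows with a correlation of 0.3 between the covariates show this shrinkage.

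What the reply does not supply is a reason for the cuts in the ANCOVA itself. The protocol gives none, and a pre-specified curved term answers the linearity argument.

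**Conclusion.** The point holds as a small, optional improvement. Within the assumed correlations, the categorised model's SE is about 0.15-5% larger than that of a continuous model (0.7-3.3% in the bounded simulation). This is worth about 1 to 31 of 300 patients and at most about one point of power. Every scenario stays above the stated 90%. Because the residual variance is common to all arms, the same SE ratio applies to each dose against placebo and to the combined doses.

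The size rests on correlations that the protocol does not give and on a roughly monotone relation between VFDs and the covariates. Weak correlations make the loss negligible. The two-level age cut loses a larger share of its covariate's information than the quartiles do. The documents do not support calling the planned analysis biased, invalid or underpowered.

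**What to change.** In 13.3.4 and the synopsis, and so in 13.3.6, enter baseline age and baseline APACHE II as continuous covariates, keeping region and baseline ventilation as factors. Fix the functional form before unblinding, for example linear plus quadratic or a restricted cubic spline, and do not let a test on the data choose between forms. Linear plus quadratic for both covariates uses four parameters, the same number as the present three for APACHE II quartiles and one for age.

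Retain the existing categories for the Cochran-Mantel-Haenszel and log-rank strata and for the subgroup plots by covariate level.

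The change needs no new data or patients, and 13.1 has the SAP finalised before the last patient visit, so there is a natural place to record it. The downside is one or two model terms to justify, and ANCOVA covariates that no longer match the mortality strata exactly.
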